5.5.1. Pharmacokinetic/Pharmacodynamic

The relationship between trough concentration of GSK2982772 and target engagement in both plasma/blood and skin (data permitting) will be investigated graphically using scatter plots.

Exploratory plots may be presented for individual and/or pooled plasma concentration versus change from baseline and/or absolute PASI score.

A population analysis will be implemented by CPMS to describe the PASI score (change from baseline and absolute) versus time course (up to Week 12) using a longitudinal model in order to predict the PASI score and the derived PASI75 at Week 16 (additional time point of interest for comparison to competitors). The model structure will be dependent on the emerging data.

If data permit, potential relationship between trough concentration of GSK2982772 and PASI score will be studied. PASI scores (change from baseline and absolute) over time (up to Week 12 (Day 85)) will be modelled in order to predict the PASI score at Week 16 using a non-linear mixed effect approach. Exposure-response may also be evaluated for other efficacy or PD biomarkers. This work will be conducted by the GSK DMPK group and will not form part of the CSR delivery.

5.6. Exploratory Endpoint(s) Analyses

5.6.1. Pharmacodynamic

Pharmacodynamic analysis will be conducted on the Safety population.

Target engagement of RIP1 kinase is defined as the percentage reduction of Free/Total relative to baseline. Target engagement in both blood and skin will be summarized by treatment group and visit.

Line plots of both individual and average target engagement by treatment group will be presented over time for both skin and blood. Boxplots of the target engagement data by visit and treatment may also be produced.

A Bayesian MMRM analysis of the log difference in ratio of free to total RIP1 will be used to analyse target engagement in the blood and skin over time (details given in [Table 5](#)).

Following the implementation of Protocol Amendment 3, skin biopsies to be used to assess target engagement in the skin are not required. The MMRM analysis of skin target engagement outlined above may not be produced if only limited skin data is available.

Table 5 Statistical Analysis of Continuous Exploratory Endpoint(s)

Endpoint(s)	

 • Log(Ratio) – Baseline log(Ratio) in the blood at Week 12 (Day 85) • Log(Ratio) – Baseline log(Ratio) in the skin at Week 12 (Day 85). 	
Where Ratio = Free RIPK1/Total RIPK1	
Analysis method	
Bayesian GLMM with natural link (MMRM equivalent)	
Model Specification	
Outcome	y_i = vector of change from baseline for participant i
Predictors	
 • Treatment (categorical) • Visit (categorical) • Treatment*visit (categorical) • Prior Biologic Use (categorical) • Baseline (on log scale) (continuous) • Baseline (on log scale)*visit (continuous) 
Unless stated otherwise the predictors (not including study treatment or visit) will be centered around their estimated mean prior to inclusion in the model

Model	$y_i \sim MVNormal(\mu_i, \Sigma)$ $\mu_i = X_i \beta$
Prior distributions for coefficients (β)	β = fixed effect parameters associated to predictors β_k : non-informative prior of $N(0, SD=100)$
Prior distributions for random effects (b)	$\Sigma \sim$ Inverse Wishart (J, S), with J = number of visits (degree of freedom), S = identity matrix Note: If convergence issues occur, an alternative covariance matrix structure may be used, for example a compound symmetric structure, to help improve convergence.
Model Checking & Diagnostics	
See Section 5.1.1	
Results Presentation	

 • Adjusted ratios to baseline and 95% CrI will be derived using the following transformation: $\exp(\text{posterior mean})$ for each treatment group • Percentage target engagement will be calculated using the formula: $(1 - \text{Adjusted ratio}) * 100\%$. • Ratios to placebo and 95% CrI will be calculated by back-transforming ($\exp()$) the difference in posterior means and associated 95% CrI. This will be used to derive the percentage reduction in Free/ Total for GSK2982772 compared to placebo. • Summary tables and figures produced will include results for earlier timepoints in addition to Week 12 (Day 85). 	

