
compared with placebo in participants with moderate to severe plaque psoriasis.
	
 PASI75 response (achieving ≥75% improvement from Baseline in PASI score) at Weeks 2, 4, and 8. PASI50, PASI90 and PASI100 response (achieving ≥50%, ≥90% and 100% improvement from Baseline in PASI score respectively) at Weeks 2, 4, and 8. Change from Baseline PASI scores at Weeks 2, 4, 8. 
Static Investigator's Global Assessment (sIGA):
 
 sIGA response (achieving a sIGA score of CCI (0) or CCI (1)) at Weeks 2, 4, and 8. sIGA score category at Weeks 2, 4, 8, 12. 
Body Surface Area (BSA):
 
 Change from Baseline in BSA at Weeks 2, 4, and 8.

 To investigate effect of GSK2982772 960 mg MR QD for 12 weeks, on pathway and target engagement, transcriptomic profiling, inflammatory, and metabolic biomarkers in the skin and blood of participants with moderate to severe plaque-type psoriasis. 	
Pharmacology biomarker endpoints:
 
 Target Engagement Assay RIP1 (TEAR1) in blood at Weeks 0, 4, and 12. 
Transcriptomic profiling:
 
 Transcriptomic analysis, including but not limited to ribonucleic acid sequencing (RNA-seq), of messenger ribonucleic acid (mRNA) isolated from skin at Weeks 0, 4, and 12, with any changes in specific inflammatory gene transcript levels (e.g. IL-4, IL-10, IL-17, IL-21, IL-22, TNF and IFNγ) possibly being evaluated. 
Inflammatory and Keratinocyte biomarkers:
 
 Change from Baseline in histopathological scoring of psoriatic lesional biopsies, which may include, but are not limited to the following at Weeks 0, 4, and 12: epidermal thickness, keratin 16 (K16), antigen Ki-67 (Ki67), CD3, cluster of differentiation 11c (CD11c). Change from Baseline in inflammatory protein markers in blood which may include but are not limited to the following at Weeks 0, 4, and 12: IL-17, chemokine ligand 20 (CCL20), IL-6, IL-8, IL-4, C-X-C motif chemokine 10 (CXCL10). 
Metabolic biomarkers
 
 Change from Baseline in metabolic markers in fasting blood which may include but are not limited to the following at Weeks 0, 4, and 12:

Objectives	Endpoints
	homeostatic model assessment of insulin resistance (HOMA) (glucose and insulin), glycated hemoglobin (HbA1c), lipid panel.

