5. STATISTICAL ANALYSES

5.1. General Considerations

Unless otherwise specified, the Enrolled or Randomised Analysis Sets will be used for all Study Population analyses (detailed in the OPS), the Intent to Treat Set will be used for all Efficacy analyses, PK Set will be used for PK analyses and Safety Analysis Set will be used for all safety and PD analyses, COVID specific outputs as well as a subset of safety analyses will be produced using the COVID population.

In the case of wrong stratification assigned at the time of randomization, the analyses will be performed based on the data collected in the electronic case record form (eCRF), not the assigned stratum at randomization.

Credible intervals (CrI) will be equal-tailed and use 95% level unless otherwise specified.

Unless otherwise specified, summary tables will provide the following descriptive statistics as a minimum:

- Continuous data (normally distributed):
n, mean, standard deviation (SD), median, minimum and maximum.
- Continuous data (log-normally distributed):
n, geometric mean, SD on the log scale (SD (log)), median, minimum and maximum.
- Categorical data:
number and percentage of participants in each category.

Figures of average responses to primary and secondary endpoints for each treatment group over time will be produced including a suitable measure of uncertainty. Adjusted (posterior) values will be used where available.

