Results Presentation	

 Posterior medians and 95% CrI of true response rate for each treatment group. Posterior medians and 95% CrI for the true difference in proportion of responders (GSK2982772 – placebo) and odds ratios of GSK2982772 to placebo. Probabilities that the true treatment difference is greater than a range of values of interest (e.g. 0%, 20%, 45%, 55%). See OPS outputs list for details. Probabilities that the true response rate on active is greater than a range of values of interest (e.g. 0%, 30%, 55%). See OPS outputs list for details. 	
Interim Analysis	

The interim analysis will estimate the predictive probability of meeting various decision criteria including:
 
 >55% probability that true difference in PASI75 response (GSK2982772 – Placebo) above 45% >97.5% probability that true difference in PASI75 response (GSK2982772 – Placebo) above 0% 	

Predictive probabilities will be calculated via simulation assuming a total sample size of 21 (14:7 for GSK2982772:Placebo).

The parameter posterior distributions from the Bayesian logistic regression analysis of interim data will be used to simulate predicted PASI75 responses for remaining trial subjects. For participants yet to be enrolled, average covariate values will be assumed.

The predicted data will be combined with the observed interim data and the Bayesian logistic model applied to assess the decision criteria. This process will be repeated for each run of the MCMC procedure. The proportion of times the decision criteria is met will be the predicted probability.

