Model	$y_i \sim \text{Ber}(p_i)$ $\text{logit}(p_i) = (\text{Treatment}=\text{Placebo}) \times \beta_1 + (\text{Treatment}=\text{GSK}) \times \beta_2 + (\text{Prior Biologic Use}^*) \times \beta_4 + (\text{Baseline PASI score}^*) \times \beta_5$
Prior distributions for coefficients (β)	β = fixed effect parameters associated to predictors 
 • β_1 & β_2: non-informative prior such that $\text{logit}^{-1}(\beta_k) \sim \text{Beta}(1/3, 1/3)$ • Other β_k: non-informative priors of $N(0, \text{SD}=100)$
Model Checking & Diagnostics	
See Section 5.1.1	
Results Presentation	

 • Posterior medians and 95% CrI of true response rate for each treatment group. • Posterior medians and 95% CrI for the true difference in proportion of responders (GSK2982772 – placebo) and odds ratios of GSK2982772 to placebo. • Probabilities that the true treatment difference is greater a range of values of interest (e.g. 0, 20, 40). See OPS outputs list for details. 	

Table 4 Statistical Analysis of Continuous Secondary Endpoint(s)

Endpoint(s)	

 • Change from Baseline PASI scores at Week 12 (Day 85) • Change from Baseline in psoriatic BSA at Week 12 (Day 85) 	
Analysis Method	
Bayesian GLMM with natural link (MMRM equivalent)	
Model Specification	
Outcome	y_i = vector of change from baseline for participant i
Predictors	
 • Treatment (categorical) • Visit (categorical) • Treatment*visit (categorical) • Prior Biologic Use (categorical) • Baseline (continuous) • Baseline*visit (continuous) 
Unless stated otherwise the predictors (not including study treatment or visit) will be centered around their estimated mean prior to inclusion in the model

Model	$y_i \sim MVNormal(\mu_i, \Sigma)$ $\mu_i = X_i \beta$
Prior distributions for coefficients (β)	β = fixed effect parameters associated to predictors 
 • β_k: non-informative prior of $N(0, SD=100)$
Prior distributions for random effects (b)	
 • $\Sigma \sim$ Inverse Wishart (J, S), with J = number of visits (degree of freedom), S = identity matrix 
Note: If convergence issues occur, an alternative covariance matrix structure may be used, for example a compound symmetric structure, to help improve convergence.

Model Checking & Diagnostics	
See Section 5.1.1	
Results Presentation	

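### The identity-scale inverse-Wishart prior in SAP Table 5 is not vague on a log scale and could widen the credible intervals for blood target engagement

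*SAP*

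**What the plan says.** SAP section 5.6.1, Table 5, fits a Bayesian repeated-measures model to change from baseline in the log of a ratio ("Where Ratio = Free RIPK1/Total RIPK1"). The residual covariance matrix has an inverse-Wishart prior "with J = number of visits (degree of freedom), S = identity matrix". SAP section 5.3.2, Table 4, gives the identical prior for change in PASI score and change in psoriatic BSA. Neither table rescales S or standardises the outcome.

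Only J differs between outcomes. Target engagement in blood is scheduled as "Target Engagement Assay RIP1 (TEAR1) in blood at Weeks 0, 4, and 12", which leaves two post-baseline visits. PASI and BSA have four: Weeks 2, 4 and 8, plus Week 12.

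Intervals follow SAP section 5.1: "Credible intervals (CrI) will be equal-tailed and use 95% level unless otherwise specified". In Table 5 they are exponentiated to give a ratio to placebo and a percentage reduction.

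**The concern.** An inverse-Wishart scale matrix is expressed in the squared units of the outcome. An identity matrix therefore says something quite different about PASI points, percentages of body surface and log ratios. With J degrees of freedom the prior acts like one extra residual with variance about 1. That is trivial when the SD is several units and not trivial when it is a few tenths.

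Blood target engagement is measured in all participants and is the only target-engagement matrix still required after Amendment 3. If PASI75 is negative, it helps to separate failure to engage RIPK1 from engagement without benefit. The width of its interval should come from the data.

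Nothing in the SAP is set up to detect the effect:
- The vague-prior sensitivity analysis (SAP 5.1.1 and 5.2.3) is tied to informative priors, and this prior is not labelled as one.
- The alternative covariance structure in Table 5 is triggered only by convergence problems. A model with this prior can converge perfectly well and still be influenced by it.
- Section 5.6.1 lists no sensitivity analysis for the target-engagement model.

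**Working it through.** The documents give no residual SD, interval width or power for these models, so there is no figure of theirs to reproduce.

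**Inputs.** From the SAP: the inverse-Wishart(J, I) prior and the model terms (Table 5), N(0, SD=100) priors on coefficients (Table 5), 21 participants split 14:7 (Table 2, interim analysis), and 95% equal-tailed intervals (5.1). Assumed: J = 2 post-baseline visits for blood, all 21 evaluable, a log-ratio residual SD between 0.2 and 1.0, and, for the simulation, a within-participant correlation of 0.5.

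**Step 1: the implied prior on one SD.** For a J × J matrix, inverse-Wishart(J, I) gives each diagonal element an inverse-gamma((J − J + 1)/2, 1/2) = inverse-gamma(1/2, 1/2) marginal, whatever J is. Equivalently, 1/SD² is chi-square with 1 df. Hence:
- 1%, 5% and 50% quantiles of SD: 0.39, 0.51 and 1.48;
- P(SD < 0.5) = P(chi-square₁ > 4) = 0.046;
- P(SD < 0.3) = P(chi-square₁ > 11.1) = 0.0009.

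**Step 2: the posterior SD.** Each visit has about 4 mean parameters (two treatment means, prior biologic use, baseline slope), leaving 21 − 4 = 17 residual df. The prior adds 1 df and a sum of squares of 1:

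posterior scale = sqrt((1 + 17·s²)/18), where s is the true SD.

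- s = 0.2: sqrt(1.68/18) = 0.306, ratio 1.53
- s = 0.3: sqrt(2.53/18) = 0.375, ratio 1.25
- s = 0.5: sqrt(5.25/18) = 0.540, ratio 1.08
- s = 1.0: sqrt(18/18) = 1.000, ratio 1.00

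The posterior median, sqrt((1 + 17·s²)/median of chi-square₁₈), is 0.311, 0.382, 0.550 and 1.019: excesses of 56%, 27%, 10% and 2%.

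**Step 3: interval width.** Two comparators were used: an ordinary REML t-interval on 17 df, and a Gibbs sampler of the Table 5 model run with S = I and with S close to zero (12 simulated data sets per setting).

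| True SD | Excess width over REML t | Gibbs width, S = I | Gibbs width, S near 0 | Excess |
|---|---|---|---|---|
| 0.2 | 52% | 0.615 | 0.394 | 56% |
| 0.3 | 24% | 0.757 | 0.598 | 27% |
| 0.5 | 8% | 1.091 | 0.988 | 10% |
| 1.0 | about 0% | 2.046 | 1.977 | 3% |

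For the Table 4 setting (J = 4) with assumed SDs of 5 and 10, SD and width each change by 0.2% or less.

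**Step 4: on the reported scale, s = 0.2.** The half-widths are about 0.31 (S = I) and 0.195 (S near 0).
- True 50% reduction versus placebo: 1 − 0.5·exp(±0.31) gives 32% to 63%, against 39% to 59%.
- True 90% reduction: 86.4% to 92.7%, against 87.8% to 91.8%.

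**The case against.** The strongest reply is that the harm is conditional. It needs a log-ratio SD well below 1, which no section states. At an SD of 1 the effect is 3% or less. This stands, and is why the sizes above are a range.

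The inflation is also largest where the interval is already tight. From the Step 3 widths, whether the interval excludes zero would change only for reductions of roughly 18–26% (SD 0.2), 26–32% (SD 0.3) or 39–42% (SD 0.5). The error is conservative. Other displays bear on the same question without this prior: raw engagement summaries and individual plots (SAP 5.6.1), concentration–engagement scatter plots (5.5.1), and trough PK with predicted engagement (5.5). The stated interim criteria concern PASI75 only. All of this stands and limits the importance of the point. It does not make the prior vague.

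Three stronger readings are tempting, and the documents do not support them:
- A reader might infer that all three outcomes are affected because they share the prior. PASI and BSA in Table 4 are modelled untransformed, where the effect is negligible. It would arise only if the log transformation that protocol 9.4.2 allows were used.
- A reader might infer a larger effect in skin, where samples would be few. SAP 5.6.1 says that model may not be produced, and no document gives a number of evaluable skin samples.
- A reader might infer that the intervals will be too wide. Without an SD for the log ratio, one can say only that they could be.

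**Conclusion.** The point holds for one analysis: the exploratory repeated-measures model of blood target engagement in SAP Table 5. Its covariance prior carries a scale of about 1 log unit and is not vague there. With 21 evaluable participants and 17 residual df, the posterior SD and interval width would be about 52–56%, 24–27%, 8–10% and 0–3% too large at assumed true SDs of 0.2, 0.3, 0.5 and 1.0. The effect is material at about 0.5 or below and negligible near 1 or above. The primary PASI75 analysis does not use this prior, and raw-scale PASI and BSA are practically untouched. This is a minor, inexpensive improvement and does not threaten the trial's conclusions.

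**What to change.** In Table 5, replace inverse-Wishart(J, I) with a half-t prior on each visit SD (for example 3 df, scale 1 on the log scale) and an LKJ prior on the correlation. In the single-visit calculation with 17 residual df, this holds the excess in the posterior median SD to about 5% or less for true SDs from 0.1 to 1.0.

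If the conjugate sampler is to be kept, pre-specify a sensitivity run with a much smaller scale matrix, for example 0.01 times the identity. Against S near zero at the same df, the remaining inflation at SD 0.2 is sqrt(1 + 0.01/(17 × 0.04)) = 1.007, under 1%.

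Make the same change in Table 4 only if PASI or BSA is log-transformed.

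Do not set S from a blinded pooled variance, because it contains the treatment difference. With 2:1 allocation it equals SD² + (2/9)·δ². At SD 0.2 and 90% engagement (δ = ln 0.1 = −2.30) that is 0.04 + 1.18 = 1.22, larger than the identity's 1.

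Cost: one table row and a small code change, with either a different sampler or one extra model run.

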5.7. Other Analyses

Additional analyses will be conducted on exploratory biomarkers including: proteomic and metabolic biomarkers in the blood, histopathological markers in the skin and transcriptomic RNA-seq data in the skin. Details of these analyses are given in the OPS.

5.8. Interim Analyses

An interim analysis (IA) is planned to occur when at least six participants on GSK2982772 have completed the Week 12 (Day 85) visit or withdrawn from study treatment. The purpose of the IA is for internal decision making about future GSK2982772 trials and assess futility. The study may be stopped for futility if the probability of a positive outcome at the end of the trial is low based on the data available at the IA. The trial cannot be stopped early based on positive efficacy data.

Predictive probabilities will be calculated via simulation. The parameter posterior distributions from the Bayesian logistic regression analysis of interim data will be used to repeatedly simulate PASI75 response for remaining trial subjects. The predicted data will be combined with interim data to assess end of study criteria and calculate the proportion of times the decision criteria are met.

The data will be reviewed by an internal Data Review Committee. The committee will include the study statistician, the study pharmacokineticist and a limited number of GSK staff. A DRC charter will identify the specific staff to form part of the DRC, as well as detail the data to be reviewed, planned analyses, guidelines for the decision rules to be followed and a dissemination plan for interim decisions.

A subset of the outputs for the end of study will be produced for the IA. These will focus on efficacy data including, but not limited to:

- Summaries of PASI response data and change from baseline in PASI score by treatment and visit as outlined in Section [5.3.2](#) (Modified ITT population).
- Bayesian analysis of PASI75 response at Week 12 (Day 85) as outlined in Section [5.2.2](#) (Modified ITT population).
- Summaries of PK data and predicted target engagement as outlined in Section [5.5](#) (PK population).
- Summary of longitudinal model used to predict PASI score and the derived PASI75 at Week 16, outlined in Section [5.5.1](#), (conducted by CPMS on the ITT population).
- Summaries of disposition and psoriatic baseline characteristics (Randomised population).

Safety monitoring of blinded data will be conducted by the internal GSK Safety Review Team (SRT) at regular intervals throughout the study, see Section 8.2 of Protocol.

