9.4.1. Primary Analyses

Efficacy analyses will be based on the ITT population unless stated otherwise in the SAP. The primary analysis will assess the difference in PASI75 response rates between GSK2982772 960 mg and placebo at Week 12. A Bayesian logistic regression analysis of the difference in PASI75 response rates at Week 12 will be conducted to calculate posterior probabilities that the true effect of GSK2982772 relative to placebo is greater than a range values of interest.

An informative prior will be used for the placebo arm to leverage relevant historical placebo data into the analysis. It is expected that this prior will be a Beta (3.5, 46.5)

distribution, giving the historical data an effective sample size of 50 participants. Further emerging placebo data may be incorporated into the prior distribution for the placebo arm prior to breaking the study blind. A non-informative prior will be used for the PASI75 response rate on GSK2982772.

Participants who discontinue early or have missing PASI data at any visit will be treated as PASI75 non-responders at that time point (regardless of their response at previous visits). Sensitivity analyses will be conducted to investigate the impact of this approach to handling missing data.

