9.5. Interim Analyses

An interim analysis is planned to occur when at least six participants on GSK2982772 have completed the Week 12 visit or discontinued study treatment to aid internal decision making around subsequent GSK2982772 trials. The study may be stopped for futility if the probability of a positive outcome at the end of the trial is low based on the data available at the interim. There is no plan to stop the trial early based on positive efficacy data.

The data will be reviewed by an internal DRC. The committee will include the study statistician, the study pharmacokineticist and a limited number of GSK individuals. The charter will identify the specific individuals to form part of the DRC, as well as detail the data to be reviewed, planned analyses, guidelines for the decision rules to be followed and a dissemination plan for interim decisions.

The interim will focus on efficacy data including, but not limited to, PASI response rates and change in PASI score from Baseline.

The SAP and data review charter will describe the planned interim analyses in greater detail.

Safety monitoring of blinded data will be conducted by the internal GSK Safety Review Team (SRT) at regular intervals throughout the study, see Section 8.2.

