4. ANALYSIS SETS

Analysis Set	Definition / Criteria	Analyses Evaluated
Screened	
 • All participants who were screened for eligibility 	
 • Study Population
Enrolled	
 • All participants who signed the ICF, passed screening and were eligible for randomisation (regardless of whether the participant went on to be randomised). • Note screening failures (who never passed screening even if rescreened) and participants screened but never enrolled into the study (Reserve, Not Used) are excluded from the Enrolled analysis set as they did not enter the study. 	
 • Study Population
Randomised	
 • All participants who were randomly assigned to study intervention in the study. • Participant must have signed ICF and passed Screening. 	
 • Study Population

Analysis Set	Definition / Criteria	Analyses Evaluated
	
 • Data will be reported according to the randomised study intervention. 	
Intent to Treat (ITT)	
 • All participants who were randomised to study intervention in the study and who received at least one dose of study intervention. • Data will be reported according to the randomised study intervention. 	
 • Efficacy
Modified Intent to Treat (ITT)	
 • All participants in the ITT population who completed at least the Week 4 assessment. • Data will be reported according to the randomised study intervention. 	
 • Efficacy
Safety	
 • All participants in the enrolled population who received at least one dose of study intervention. • Data will be reported according to the actual study intervention received. 	
 • Safety • PD
COVID-19	
 • All participants in the Safety set who had a confirmed, probable or suspected COVID-19 case diagnosis. 	
 • COVID outputs

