5.2.2. Main analytical approach

The primary analysis will be produced for the ITT population.

The summary measure of interest is the difference in PASI75 response rates at Week 12 (Day 85) between GSK2982772 and placebo. Missing values will be imputed as non-responders.

The primary endpoint will be analysed using a Bayesian logistic regression model, details given in [Table 2](#). Summary statistics will be provided for the posterior distribution of the true difference in PASI75 response rate (GSK2982772 vs placebo) as well as posterior probabilities for a range of thresholds.

A non-informative prior will be used for the PASI75 response rate on GSK2982772 and covariates.

An informative prior will be used for the placebo response rate of the form: 90% weight on $Be(5.39, 69)$ and 10% on $Be(1/3, 1/3)$. The prior was derived from historical data from similar clinical trials using meta-analytic predictive prior (MAP) approach, the effective sample size is approximately 63 [[Schmidli, 2014](#)].

In the event that the placebo prior is different from what is presented here, this will be documented in the CSR.

Table 2 Statistical Analysis of Primary Endpoint

Endpoint(s)	

 PASI75 response at Week 12 (Day 85) 	
Analysis Method	
Bayesian Logistic Regression (using informative prior)	
Model Specification	
Outcome	$y_i = \text{Response (0/1) for participant } i$
Predictors	
 Treatment (categorical) Prior Biologic Use (categorical) Baseline PASI score (continuous) 
Unless stated otherwise the predictors (not including study treatment) will be centered around their estimated mean prior to inclusion in the model

Model	$y_i \sim \text{Ber}(p_i)$ $\text{logit}(p_i) = (\text{Treatment=Placebo}) \times \beta_1 + (\text{Treatment=GSK}) \times \beta_2 + (\text{Prior Biologic Use}^*) \times \beta_4 + (\text{Baseline PASI score}^*) \times \beta_5$
Prior distributions for coefficients (β)	β = fixed effect parameters associated to predictors 
 β_1: informative prior such that $\text{logit}^{-1}(\beta_1) \sim$ mixture of Betas* β_2: non-informative prior such that $\text{logit}^{-1}(\beta_2) \sim \text{Beta}(1/3, 1/3)$ Other β_k: non-informative priors of $N(0, SD=100)$ 
*Expected prior is a mixture of $Be(5.39, 69)$ and $Be(1/3, 1/3)$, weighted to 90% and 10% respectively. Final prior will be reported in the CSR.

Model Checking & Diagnostics	
See Section 5.1.1	

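### The interim trigger over-samples discontinuations while the Modified ITT set drops the early ones, so the predictive probability is distorted in a direction the plan does not fix

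*SAP*

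**What the plan says.** - **Trigger.** SAP 5.8 has the interim "planned to occur when at least six participants on GSK2982772 have completed the Week 12 (Day 85) visit or withdrawn from study treatment". Protocol 9.5 likewise sets it "when at least six participants on GSK2982772 have completed the Week 12 visit or discontinued study treatment". The same rule stands in Protocol 1.1 and 4.1 and in SAP 1.3.
- **Scoring.** Protocol 9.4.1: "Participants who discontinue early or have missing PASI data at any visit will be treated as PASI75 non-responders at that time point". SAP 5.2.2: "Missing values will be imputed as non-responders".
- **Interim analysis set.** SAP 5.8 assigns the interim Bayesian analysis of Week 12 PASI75 to the "Modified ITT population", defined in SAP 4 as "All participants in the ITT population who completed at least the Week 4 assessment".
- **Final analysis set.** SAP 5.2.2: "The primary analysis will be produced for the ITT population".
- **Prediction.** SAP 5.2.2, Table 2: the "parameter posterior distributions from the Bayesian logistic regression analysis of interim data will be used to simulate predicted PASI75 responses for remaining trial subjects". The total is taken as 21 (14:7). No adjustment for time at risk is described.
- **Decision.** SAP 5.8 allows stopping if the probability of a positive final outcome is low. It gives no number and leaves decision guidelines to the committee charter.

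**The concern.** A failure by discontinuation can resolve within days of entry. A response resolves only at the Week 12 visit (Day 85, window 3 days either way). With staggered entry, the first six active participants to resolve therefore include recent entrants who stopped, but not the entrants of the same weeks who are still on treatment. Their posterior is then used to simulate everyone else.

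The interim set works the other way. A participant who stops before Week 4 and has no Week 4 assessment helps to trigger the look, is absent from the interim model, and is a failure in the final ITT analysis. The trigger, the interim model and the final analysis thus rest on three different sets of participants.

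The predictive probability is the futility statistic, and with about six active participants it is sensitive to a single outcome.

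**Working it through.** **Inputs from the documents.** Active 62% and placebo 7% (SAP 3); 14:7 participants; active prior Beta(1/3, 1/3); design placebo prior Beta(3.5, 46.5) (SAP 3); analysis placebo prior 0.9 Be(5.39, 69) + 0.1 Be(1/3, 1/3) (SAP 5.2.2); criteria P(difference > 45%) > 55% and P(difference > 0) > 97.5% (Table 2).

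**Assumptions, because the documents give no figure.** Poisson accrual; discontinuation uniform over 12 weeks unless stated; overall active response held at 62% with discontinuers as failures; participants not yet at Week 12 simulated rather than scored; those stopping before Week 4 have no Week 4 assessment; no covariates or replacements.

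**1. The plan's own figure.** Sum Bin(14, 0.62) × Bin(7, 0.07) over outcomes meeting the > 0 criterion. Result: 99.7% with Beta(3.5, 46.5) and 98.1% with the mixture prior. The stated value of approximately 99% reproduces. It describes the end of the trial; the documents give no such figure for the interim.

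**2. Sensitivity of the statistic.** For 0 to 2 placebo responders the 45% criterion needs about 8 of 14 active responders. With x responders of 6, the predictive probability is P(Y ≥ 8 − x), where Y follows a beta-binomial(8; x + 1/3, 6 − x + 1/3). For x = 0 to 6 this gives 0, 0.006, 0.092, 0.410, 0.807, 0.978 and 1.000.

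**3. Trigger alone.** Let a participant resolve at entry + D weeks if discontinuing at week D, otherwise at entry + 12. The look falls at the sixth resolution on active. With one active entry per week and 15% discontinuing, discontinuers are 26% of the six (26/15 = 1.7 times their true share). If all six entered the model, response would average 0.54 and predictive probability 0.51, against 0.62 and 0.64 for an unselected cohort. This is not the SAP's analysis, because of step 4.

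**4. Modified ITT alone.** Under uniform timing a fraction d × 4/12 of active participants leaves the set, so the true response within it is 0.62/(1 − d/3). At d = 15%: 0.62/0.95 = 0.653. At d = 22%: 0.62/0.927 = 0.669. The set is optimistic relative to ITT before the trigger acts.

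**5. Both together.** Mean predictive probability, 45% criterion, by simulation:

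| Active accrual | Discontinuing | Current trigger, Modified ITT (SAP) | Day-85 cohort, Modified ITT | Day-85 cohort, ITT |
|---|---|---|---|---|
| one per week | 15% | 0.60 | 0.68 | 0.64 |
| two per week | 22% | 0.51 | 0.70 | 0.64 |
| one per 2 weeks | 15% | 0.64 | 0.68 | 0.64 |
| one per 3 weeks | 15% | 0.66 | 0.68 | 0.64 |
| one per week, all after Week 4 | 15% | 0.54 | 0.64 | 0.64 |

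Entries are approximate; separate runs agreed to about 0.01. Within the same set, the trigger lowers the value in every row (third column against fourth). Against the ITT target (last column), the net shift is downward, nil or slightly upward.

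**6. Size of the interim model.** Early discontinuers count towards the six but leave the model, which then holds about 5.0 to 5.8 active participants on average.

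**7. The > 0 criterion.** A simulation of both arms with the mixture prior shows smaller movement. At 10% discontinuing and 8 randomised per month the mean is 0.878 under the SAP's rule and 0.898 for a Day-85 ITT cohort (difference 0.020). At 20% it is 0.852 against 0.903 (difference 0.051).

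**The case against.** A reader might infer from the trigger that the interim is biased towards futility and that an effective drug could be stopped because of the order in which outcomes arrive. The documents do not support that as a general statement. Modified ITT removes many of the earliest discontinuers, who drive the asymmetry. On that set the case in step 3 moves from 0.51 back to about 0.60, and at one active entry per two or three weeks the downward shift disappears or reverses. With no stated cut-off, no change in the chance of stopping can be calculated.

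Other points favour the plan. The protocol describes discontinuation of treatment as rare (7.1) and withdrawal as uncommon (7.2). At 10% discontinuing, or with slow accrual, the effect is small. The committee also sees PASI summaries by visit and a longitudinal model on the ITT population, so ongoing participants are not invisible to it.

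All of this stands as a limit on size and direction, but it does not make the rule sound. Any cancellation is accidental, and it fails if discontinuations fall mainly after Week 4 (0.54 in step 5). Protocol 7.1 also keeps participants in the study after they stop treatment. Someone who stops early but attends Week 4 remains in Modified ITT, which weakens the offset. The SAP's version history itself says the chance of dropout unrelated to the trial has risen with COVID-19.

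**Conclusion.** The concern holds as a mismatch between the trigger, the interim set and the final set. The trigger over-samples discontinuers, Modified ITT drops some whom the final ITT analysis counts as failures, and the net error in the predictive probability has no fixed sign. Under the assumptions above it runs from about 0.13 too low (0.51 against 0.64) to about 0.02 too high (0.66 against 0.64) on the 45% criterion, and less on the > 0 criterion. These sizes rest on assumed accrual and on assumed discontinuation rate and timing. A one-directional bias towards futility, or a stated rise in wrongful stopping, is not established. The point is worth correcting before the look because the correction is cheap and removes the dependence on those unknowns.

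**What to change.** Change the trigger and the analysis set together:

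1. Trigger the interim *when at least six participants on GSK2982772 have passed their scheduled Day 85 date, whether or not they completed treatment*.
2. In SAP 5.8, replace Modified ITT for the interim PASI75 model by all ITT participants in both arms who have passed that date, completers and discontinuers alike. This matches the final analysis.
3. Simulate all other participants as remaining subjects.
4. Use the same trigger wording in Protocol 1.1, 4.1 and 9.5 and in SAP 1.3 and 5.8.

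In the simulations this restored about 62% response and a predictive probability of about 0.64 at every accrual and discontinuation rate tried. Changing the trigger alone and keeping Modified ITT would leave an optimistic value (about 0.68 at 15% discontinuing).

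The cost is revised wording and a look that comes about 0.2 to 1.3 weeks later on average.
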